9.4.4 Safety Analyses

Safety measures will be reported as summary statistics during treatment, with shift tables provided for laboratory measures taken at baseline and end of study. Adverse events will be coded using the version of MedDRA available at the start of the trial. Each AE will be counted once for each subject unless it resolves and recurs, in which case it may appear as multiple AEs. Severity, frequency, and relationship of AEs to study intervention will be presented by System Organ Class (SOC) and preferred term groupings.

Listings will be provided for discontinuations, deviations, compliance, AEs leading to discontinuation, and AEs related to the index ulcer. AE listings will include severity and relationship to test article, as well as actions taken.

Tables will be provided summarizing reasons for screen failure, reasons for premature discontinuation, protocol deviations, subject compliance, treatment emergent AEs (TEAEs), TEAEs of interest, TEAEs by severity, SAEs, and AEs leading to discontinuation as well as total score of Cardiff Wound Impact Schedule (CWIS).

Where applicable, analyses of safety measures will be conducted, respectively, for the 26-week treatment period of the safety population and for the long-term observation period of the LO population. Missing values in safety measures will remain as missing in analyses.

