1.2 Study Schematic

Study schematic showing the overall flow of visits, and the main procedures carried out at the various visits. Monthly follow-up visits begin after confirmation of healing, or after the first 26 weeks for wounds not healed by then.

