8.1.9 Confirmation of Closure ("C" Visits)

[Purpose:] These visits serve to confirm that a wound has achieved complete closure

Confirmation of Closure visits are used to record the initial observation of closure, and persistent closure. Ideally, a wound that shows initial closure will still be closed at a confirmation visit two weeks later, and at a second confirmation visit four weeks later. At each of the confirmatory visits, use the Confirmation of Closure visit form(s) to record observations. Continue with the off-loading device appropriate to the location of the ulcer during the period of confirmatory visits.

Perform the following procedures:

- Assess adverse events
- Review concomitant medications
- Assess subject compliance regarding off-loading since the last visit

- Obtain photographs of the ulcer using the electronic wound imaging and measuring device
- Observe the wound if it is fully epithelialized with no drainage or need for a dressing, record it as closed.

If the wound is found to be open at either confirmation visit or if the subject misses a scheduled confirmation visit, record it as such and then move directly to the original schedule of visits. This may become a treatment visit for example if the subject has not passed Visit 16, or an observation visit if the subject has passed Visit 16.

If the index ulcer is closed at the first confirmation visit, schedule the subject to return for a second consecutive confirmation visit in 14 ± 2 days. If the index ulcer remains closed at the second confirmation visit, schedule the subject to begin the Long Term Observation Period at the next study day that will put the subject onto the planned 28 day schedule of visits. For example, if a subject completes the second confirmation visit on Day 50, they should return on Day 64 and continue thereafter with visits every 28 ± 3 days. Days 92, 120, 148, 176, 204, or 232 are the other days on which these subjects can enter into Long Term Observation. Note that Day 176 has a unique window of plus or minus 2 days, otherwise these visits have windows of plus or minus 3 days.

If the initial closure is observed at Visit 28 or 29, the subject should move immediately to the End of Study procedures once both confirmation visits are completed, or if the wound is found to be open at either of the two confirmatory visits.

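### The long-term safety window starts at confirmed closure for healed subjects (from Day 64) but after Visit 23 for unhealed ones, so its length depends on the primary outcome and it overlaps the 26-week safety period

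*Protocol*

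**What the plan says.** Section 9.4.4 splits the safety analyses, where applicable, into two parts: "for the 26-week treatment period of the safety population and for the long-term observation period of the LO population". Events are tallied by subject ("Each AE will be counted once for each subject unless it resolves and recurs"). The section gives no start day for the second period and no allowance for time at risk.

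The start of that period is found in the visit procedures. When closure is confirmed at the second confirmation visit, Section 8.1.9 tells the site to "schedule the subject to begin the Long Term Observation Period at the next study day" that fits the 28-day grid. Its example is that "if a subject completes the second confirmation visit on Day 50, they should return on Day 64", and it adds that "Days 92, 120, 148, 176, 204, or 232 are the other days on which these subjects can enter into Long Term Observation". Section 8.1.6 books an unhealed subject's first long-term visit 28 days after Visit 23. The schematic in Section 1.2 gives the same two-way rule: "Monthly follow-up visits begin after confirmation of healing, or after the first 26 weeks for wounds not healed by then". Section 8.1.7 places healed and unhealed subjects in the same period.

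Three other places mark the period differently. Section 9.3 defines the LO population by Visits 22 to 26, Section 8.1.7 uses Visits 24 to 28, and footnote g of the Schedule of Activities refers to open wounds through Visit 21.

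**The concern.** A safety period should start at the same point for everyone, or at least at a point treatment cannot move. Here it starts at healing, which is the primary endpoint. If TTAX01 speeds closure, more of its subjects enter early and that arm accrues more long-term time. A proportion of subjects with an event rises with time at risk, so the two arms can differ in the long-term table when their true event rates are the same.

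The second problem does not depend on any treatment effect. Nothing ends the 26-week period when a subject enters long-term observation. An early healer's events between Day 64 and the end of the 26 weeks therefore belong to both periods, and the two summaries are not a partition of the study.

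**Working it through.** **Calendar.** Start at Day 1, with 7-day steps to Visit 20, 14-day steps to Visit 23 and 28-day steps to Visit 29:
- Visit 9 = 1 + 8×7 = Day 57 (agrees with Section 6.5).
- Visit 20 = 1 + 19×7 = Day 134.
- Visit 23 = 134 + 3×14 = Day 176.
- Visit 24 = 176 + 28 = Day 204.
- Visit 29 = 204 + 5×28 = Day 344 (agrees with Section 8.1.8).

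**Earliest entry.** In the protocol's own example the second confirmation visit is on Day 50, so closure was first seen on Day 50 − 28 = Day 22 (Visit 4), and entry is on Day 64. Closure at Visit 2 (Day 8) gives a second confirmation on Day 36 and, again, entry on Day 64.

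**Length of the window, to Day 344**
- Earliest healer: 344 − 64 = 280 days, with 280/28 + 1 = 11 visits.
- Non-healer from Visit 24: 344 − 204 = 140 days, with 6 visits. Counted from Visit 23: 344 − 176 = 168 days.
- Ratio: 280/140 = 2.0, or 280/168 = 1.7.

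**Overlap with the first period.** If that period ends at Visit 23, the overlap is 176 − 64 = 112 days. If it ends 26 weeks after Day 1 (Day 183), it is 183 − 64 = 119 days.

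**Effect for one subject.** With a constant rate r per year, P(at least one event) = 1 − exp(−r·L/365.25). At r = 1, L = 140 gives 31.8% and L = 280 gives 53.5%.

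**Arm averages.** Section 9.2 supplies 40% and 65% healed. Simulation: closure is seen at the next scheduled visit, second confirmation comes 28 days later, entry is on the next grid day, and everyone is followed to Day 344. Assumptions not in the protocol: no dropout, every closure confirmed, the shape of the healing-time curve, and the event rate.

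| Non-healers start | Healing-time shape | Mean days, control / TTAX01 | Ratio | Gap in event proportion at 1 per year |
|---|---|---|---|---|
| Day 204 | constant hazard | 172 / 197 | 1.14 | 37.0% vs 40.9%: 3.9 points |
| Day 176 | constant hazard | 190 / 208 | 1.09 | 40.3% vs 43.0%: 2.7 points |
| Day 204 | later healing (Weibull shape 2 to 3) | | 1.08 to 1.10 | between 1.0 and 2.8 points |
| Day 176 | later healing (Weibull shape 2 to 3) | | 1.04 to 1.06 | between 1.0 and 2.8 points |

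Some conventions for a confirmation visit that falls on a grid day bring the ratio down to about 1.03. Calibrating healing to Day 183 instead of Visit 23, under constant hazard, gives 168 and 190 days (ratio 1.13). Across the shapes tried, 24 to 37% of controls and 43 to 60% of TTAX01 subjects enter before Day 183, and the mean overlap is 11 to 22 days against 21 to 40 days.

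**Which end of the range is more plausible.** Constant hazard implies a mean closure time of about 7.1 weeks among TTAX01 subjects closing within 16 weeks. Section 2.2 reports 12.8 ± 4.3 weeks among Phase 2 healers (it is unclear whether this is initial or confirmed closure). That points to the later-healing rows.

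**Against sampling error.** With 125 per arm and a proportion near 0.39, the standard error of a difference is √(2 × 0.39 × 0.61/125) = 0.062, about 6 points.

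**After the fix.** With a common start at Day 204 every completer contributes 140 days in either arm: ratio 1.00, overlap 0.

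**The case against.** *Section 8.1.9 is scheduling text, and the statistical section goes by visit number.* This is the best counter-argument. If the long-term period were read purely by nominal visit, time at risk would be equal between arms. But Section 9.3's Visits 22 to 26 are Days 162 to 260. That range still overlaps the 26 weeks, stops before Visits 27 to 29 and disagrees with Section 8.1.7. Section 8.1.9 also says in terms that healed subjects begin the named period earlier. The protocol does not settle which reading governs.

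*This belongs to the SAP.* Section 9.4.1 does defer data conventions, and the absence of a rule for assigning events is not itself a fault. What the protocol has already fixed is a named period, its entry rule, and a safety analysis on it. A SAP that follows these faithfully inherits the problem. No sentence orders double counting; it follows from two periods that overlap with nothing to separate them. Ending the first period at entry to the second would remove the overlap, but would make both windows depend on outcome.

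*The effect is small.* This stands. Even the largest gap in the table is below one standard error. Late healers can enter on Day 204 or Day 232, with or after the unhealed.

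*The direction is open.* This also stands. A reader might infer that an effective TTAX01 must look less safe in the long term. The documents do not support that: after closure a subject is seen at 14-day confirmation visits and then every 28 days, while an unhealed subject is seen weekly to Visit 20 and every 14 days to Visit 23. Less frequent questioning may lower event capture among early healers, although Section 8.4.4 requires asking about the whole interval since the last visit.

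**Conclusion.** The point holds as a defect in how the long-term safety window is defined. Its start depends on the primary outcome, individual windows differ by up to twofold, and up to 112 to 119 days of an early healer's window also lie in the 26-week period. These follow from the protocol's own visit calendar.

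The average consequence is modest: about 3 to 14% more long-term time on TTAX01 at the planned healing rates, and roughly 1 to 4 points in event proportions at an assumed equal rate of 1 per patient-year. Both ranges assume no dropout and all closures confirmed, and vary with healing-time shape and with whether non-healers start at Day 176 or Day 204. The net direction is uncertain.

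A reader might also take this to mean that the trial's safety comparison as a whole is biased. It is not: the safety endpoint in Section 3 is the proportion of subjects with adverse events by group, with no split by period, and every subject is planned for 50 weeks. Only the period-specific summaries are affected. It is worth correcting because the remedy is nearly free and the surrounding visit references need reconciling anyway.

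**What to change.** 1. In Section 9.4.4, and in the LO population definition in Section 9.3, define both safety periods by one study-day cut that applies to every subject whether or not the wound has closed. The LO population then becomes everyone still in the study after the cut.
2. Assign each adverse event to one period only, by onset date.
3. For the second period, report exposure-adjusted rates per patient-year beside the by-arm proportions.
4. State the cut once and reconcile the references to it. Day 176 is 175 days, or 25 weeks, after Day 1, yet Section 6.5 labels Visit 23 as W26, and 26 full weeks is Day 183. Visits 22 to 26 (Section 9.3), Visits 24 to 28 (Section 8.1.7) and Visit 21 (footnote g) must also be brought into line.
5. Keep the Section 8.1.9 wording for visit scheduling only.

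The cost is a few sentences in the protocol and matching text in the SAP. Onset dates are already collected under Section 8.4.4, and no visit or procedure changes. The fix does not equalise how often subjects are asked about events before and after closure; that should be noted as a limitation when the period summaries are read.

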9.4.5 Baseline Descriptive Statistics

The following subject demographic and baseline data will be collected and reported:

Demographic variables will include but not limited to the following:

- Age
- Gender
- Ethnicity
- Race
- Smoking status

- Medical history
- Disease diagnosis, index ulcer measurement, severity, and prior treatment
- Physical examinations
- Laboratory tests
- PROMIS and CWIS QoL measures

9.4.6 Planned Interim Analyses

No interim analysis is planned for this study.

9.4.7 Subgroup Analyses

Primary and secondary efficacy endpoints will be reported by subgroup as follows:

- male vs. female
- by race based on combined categories of American Indian or Alaska Native, Asian, Black or African American, Native Hawaiian or Other Pacific Islander, and White
- by age group
- confirmed osteomyelitis vs. non-confirmed
- by baseline wound size cohort
- by use of additional therapies that were excluded prior to V9
- Use of antibiotics within first 6 weeks of treatment
- Ulcer debridement performed within first 4 and 8 weeks of treatment post initial procedure

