4 STUDY DESIGN

4.1 Overall Design

The hypothesis under study is that one or more applications over 16 weeks of TTAX01, to the wound surface of a well debrided, complex diabetic foot ulcer managed with appropriate antibiotic therapy will result in a higher probability of complete healing than would be expected from management with standard care alone. In this controlled Phase 3 trial, all subjects will receive standard care throughout the entire study, with the option to add one or more additional therapies if healing is inadequate ($\leq 50\%$ reduction in area) after 8 weeks.

Eligible consenting subjects will undergo a baseline aggressive debridement in the operating room to remove infected and devitalized bone and soft tissue. A six week course of systemic antibiotics will be used to resolve baseline infection following recommendations from the Infections Diseases Society of America (IDSA) guidelines. For subjects randomized to the treatment group, TTAX01 will be applied during the surgical procedure to the debrided wound bed at baseline, and if healing is not evident, it will be applied again at intervals no shorter than 4 week or when replacement of dislodged material is necessary. At each visit the wound will be further debrided as necessary for subjects in both groups.

Surgical debridement at the baseline visit will include biopsies of bone for histology and microbiologic testing, at the start and completion of debridement. This debridement may involve resection of necrotic bone and performance of minor amputations. Systemic antibiotics may be given empirically from the first Screening visit, with adjustments made on the basis of culture and sensitivity results. New or recurrent infections will be managed with additional debridement and adjustment or addition of appropriate systemic antibiotics. For subjects randomized to the treatment group, the test article, TTAX01, will be fixed with sutures, staples or both to the debrided wound bed at baseline and again at no less than 4 week intervals over the 16 week treatment period for wounds that do not show evidence of healing. For wounds in this group that do show evidence of healing, additional applications of TTAX01 will be withheld, week by week.

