6.5 Concomitant Therapy

In this study, the term Concomitant Medication is inclusive of all medications and therapies.

The following is excluded throughout the entire study:

• Canagliflozin, a type 2 diabetic medication, also referred to as Invokana, Invokamet, and Invokamet XR

The following are excluded through W26 (Visit 23):

- Topical antibiotics and antiseptic agents including hydrogen peroxide, acetic acid, chlorhexidine, povidone/iodine, and cetrimide
- Enzymes, negative pressure wound therapy, hyperbaric oxygen, growth factors and tissue products containing growth factors (e.g., Oasis[™]), living skin, cellular products (e.g., Apligraf[™], Dermagraft[™]), amniotic membrane and umbilical cord products
- Powdered collagen dressings (e.g., Cellerate[™]), formulated collagen dressings (e.g., Excellagen[™])
- Hyaluronic acid products (e.g., Hyalomatrix[™])
- Revascularization procedures (e.g., endoscopic perforator surgery, superficial venous ablation, endovenous laser ablation, valvuloplasty, free flap transfer with microvascular anastomoses)
- Achilles tendon lengthening

The following therapies are excluded before Visit 9 (Day 57), but allowed thereafter if the wound area is \leq 50% closed relative to the post debridement wound measurement obtained prior to randomization:

- Silver-containing products (e.g., Aquacel Ag[™], Mepilex Ag[™], Acticoat[™])
- Collagen dressings (e.g., Integra Omnigraft™, Promogran Prisma™, Puracol™, Fibracol™)

Systemic anti-microbials may be used as prescribed. Wound cleansing with a neutral, non-irritating and non-toxic solution is recommended at the discretion of the Investigator. Sterile saline, non-ionic cleanser, or hypochlorous acid are recommended.

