8.1.3 Randomization

[Purpose]: To randomly assign eligible subjects to a treatment group, with stratification, and initiate therapy.

Obtain the treatment group assignment using the computer-based randomization tool.

TREATMENT GROUP ONLY:

- Apply TTAX01 deep below the surface of the surrounding skin to cover and be in contact with the exposed tissue at the base of the wound, rough side down, and surgically fixed by sutures or staples. TTAX01 must be fenestrated prior to applying the secondary dressing. The initial application will occur as part of the surgical procedure.
 - Multiple pieces of TTAX01 may be used if required to cover the entire wound bed.
 - Obtain post-application photograph of TTAX01 using the provided electronic wound imaging and measuring device

ALL SUBJECTS (BOTH GROUPS):

- Apply wound dressing including a non-adherent, standard foam pad or alginate dressing (e.g., hydrogels, foam dressings, and alginates) that is appropriate for the amount of drainage, and a secondary bandage to ensure a moist wound environment, which adequately controls exudate and avoids maceration of the surrounding skin.
- Continue, adjust, or initiate an appropriate systemic antibiotic regimen. Topical antibiotics should not be administered. A definitive therapy will be guided by the microbiological results based on bone biopsy. An Infectious Diseases specialist may be

consulted to determine the appropriate antibiotic regimen to proceed with if the pathology report confirms the 'clean margin' is free of osteomyelitis. At least six (6) weeks of systemic antibiotic therapy is required in this protocol. If the initially chosen antibiotic is changed based on culture and sensitivity results, the total length of all antibiotic treatment will remain at 6 weeks.

Provide an off-loading device appropriate to the location of the wound with full length boot or total contact cast (unless not appropriate, where a substitute off-loading device can be made per the physician's suggestion with sponsor approval) with off-loading instructions. The substituted choice of off-loading modality should be based on the wound's location, the presence of any associated peripheral artery disease, the presence and severity of infection, and the physical characteristics of the subject.

Schedule the next Treatment Period Visit in one week $(7 \pm 2 \text{ days})$.

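### Section 9.4.7 lists three factors fixed only after randomization as efficacy subgroups; use of added therapies after Visit 9 is the one clearly open to selection bias

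*Protocol*

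**What the plan says.** Section 9.4.7 opens with "Primary and secondary efficacy endpoints will be reported by subgroup as follows" and gives eight factors. Five are baseline factors: sex, race, age group, baseline wound size cohort, and confirmed versus non-confirmed osteomyelitis (the bone biopsies are taken at the initial procedure, before randomization). The other three are observed after randomization:

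- Added therapies, entered in the list as "by use of additional therapies that were excluded prior to V9".
- Antibiotics, split on whether they were taken during the opening six weeks.
- Debridement, entered in the list as "Ulcer debridement performed within first 4 and 8 weeks of treatment post initial procedure".

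Nothing separates these three from the baseline factors or labels them descriptive. Section 9.4.1 makes superiority comparison between arms the general approach, tested two-sided at 5% unless stated otherwise. Section 9.4.9 lists no exploratory analyses.

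The rules that decide membership are elsewhere:

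- **Added therapies.** Section 6.5 bars them until Day 57 and then admits them only for a wound no more than 50% closed, with closure judged "relative to the post debridement wound measurement obtained prior to randomization". Section 4.1 describes this as standard care "with the option to add one or more additional therapies if healing is inadequate". Section 8.1.4 leaves the decision to the Investigator, and Section 6.3 says that site staff are not blinded.
- **Antibiotics.** Section 8.1.3: "At least six (6) weeks of systemic antibiotic therapy is required in this protocol".
- **Debridement.** It is part of standard care in both arms (Section 6.1.2), done as needed at each visit (Section 4.1) and on open wounds (Section 1.3, note c).

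**The concern.** A subgroup comparison keeps the protection of randomization only if membership is settled before treatment can influence it. Use of added therapies is not. It requires a poor response by Day 57 and then a choice by someone who knows the arm. A wound that closed before Day 57 and stayed closed cannot belong to a user, so early healers collect among the non-users.

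If TTAX01 accelerates early healing, as the trial hypothesizes, fewer TTAX01 subjects meet the condition and those who do are its harder cases. Control users are closer to typical control subjects. A display by arm within users, or within non-users, then compares patients of different prognosis. It could suggest that TTAX01 works less well, or not at all, alongside added therapy when no such interaction exists.

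**Working it through.** The protocol gives no figure to reproduce, so the check has two parts.

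**1. When and how each factor is fixed**

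| Factor | Fixed when | Depends on |
|---|---|---|
| Sex, race, age, wound size cohort, osteomyelitis at initial procedure | Before randomization | Nothing affected by treatment |
| Added therapies | Day 57 or later | Response of no more than 50% closure, plus an unblinded choice |
| Debridement, weeks 4 and 8 | After randomization | Wound still open and needing it |
| Antibiotics, first 6 weeks | After randomization | Required of all, so non-use means deviation or early exit |

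Only the first post-randomization factor has an explicit response condition. For debridement, every randomized wound starts open, because wounds that can be primarily closed leave as screen failures (Section 8.1.2). Most subjects may therefore count as debrided.

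**2. Illustration for added therapies**

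The plan's healing rates (Section 9.2) are 40% in control and 65% on TTAX01, which imply a hazard ratio for healing of ln(0.35)/ln(0.60) = 2.055. The remaining inputs are assumptions, run on 2,000,000 simulated subjects per scenario:

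- Prognosis U is standard normal.
- Week-8 response = U + c × treatment + noise (SD 0.7). Subjects at or below zero are eligible, and 70% of them use added therapy, which has no effect of its own.
- The log-odds of healing are −0.55 + 1.5U + b × treatment. With b = 1.35, healing is about 64% versus 40%. The treatment log odds ratio given U is constant, so there is no true interaction on that scale.

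Results with b = 1.35, as TTAX01 minus control in percentage points:

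| c | Users, TTAX01 / control | Overall | Within users | Within non-users |
|---|---|---|---|---|
| 0 | 35.0% / 34.9% | +23.5 | +24.2 | +23.2 |
| 0.5 | 23.9% / 35.0% | +23.4 | +17.3 | +21.3 |
| 1.0 | 14.4% / 35.0% | +23.3 | +9.8 | +19.0 |

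Both groups fall below the overall effect because the arms are split differently. At c = 0.5 the TTAX01 total is 0.239 × 39.9 + 0.761 × 71.3 = 63.8, and the control total is 0.350 × 22.6 + 0.650 × 50.0 = 40.4. Their difference is 23.4, yet the within-group differences are 39.9 − 22.6 = 17.3 and 71.3 − 50.0 = 21.3. Mean prognosis among users is lower on TTAX01 by 0.23 SD at c = 0.5 and by 0.48 SD at c = 1.0.

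With b = 0 (no effect on final healing) but an effect on week-8 response, users show −5.1 points (c = 0.5) or −9.7 points (c = 1.0), and non-users −2.4 or −5.1. This is apparent harm where none exists.

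A time-to-event illustration points the same way. Assuming gamma frailty with shape 1.5, a conditional hazard ratio of 2.5 (marginal 2.06) and 50% uptake among slow healers, 33.4% of control and 21.6% of TTAX01 subjects become users. The hazard ratio among users is 1.83.

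**The case against.** The strongest reply is that this is a small matter, stated too broadly if applied to all three factors. Much of that stands.

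- **Antibiotics.** A reader might infer that this split also selects on response. The documents do not support that: the course is required of everyone, so the group with antibiotics is close to the whole trial and the other group is nearly empty. The fair criticism is that the split is uninformative.
- **Debridement.** A wound that closes in week 7 may already have been debrided in week 1. In the Phase 2 study, healed wounds closed at a mean of 12.8 ± 4.3 weeks (Section 2.2), so few would close before week 4. The split is post-randomization and reflects wound status, but no bias of any size is shown for it.
- **Size.** The illustrations cover added therapies only. The shift from 2.06 to 1.83 is ln(2.06/1.83) = 0.12 on the log scale. With 125 per arm, users would number about 125 × 0.334 + 125 × 0.216 = 69. If 20 to 35 of them heal, the standard error of the log hazard ratio is about 2/√35 = 0.34 to 2/√20 = 0.45, three to four times the shift. Sampling error would exceed the bias in that illustration.
- **Use.** Section 9.4.7 speaks of reporting. It sets no interaction test and makes no claim from these groups.

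These points do not rescue the added-therapy item. Its response condition is written into Section 6.5, and Section 9.4.1 makes comparison between arms the default. An imprecise estimate that is also open to selection bias is no better for being imprecise. A statistical analysis plan might add a descriptive label, but the list itself is fixed in the protocol.

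**Conclusion.** The concern holds firmly for use of therapies excluded before Visit 9. Within users and non-users the arms lose randomized comparability if TTAX01 changes early healing, and the within-group effects are then open to selection bias. That condition matters: in the illustration there was no imbalance when treatment did not affect membership (c = 0). It would be too strong to say that the estimates are biased by a known amount. The sizes shown rest on assumed prognosis, uptake and week-8 effects, and the protocol cannot settle them.

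For debridement the point is weaker, since membership may be near-universal. For antibiotics it is that the split mainly isolates deviators and early exits and tells the reader little.

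Nor should a reader infer that the main result is compromised. The primary analysis compares all randomized subjects and does not use these groups.

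**What to change.** In Section 9.4.7, restrict treatment-effect subgroups to the baseline factors: sex, race, age group, osteomyelitis status at the initial procedure, and baseline wound size cohort. Move added therapies, antibiotics and debridement to tables of use by arm, labelled as descriptive process data, with no treatment comparison within users or non-users.

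If the added-therapy question matters, report time to first added therapy by arm and run a supplementary analysis of all randomized subjects that treats added therapy as an intercurrent event. A subgroup defined at baseline cannot stand in for it, because the therapy starts only after Day 57.

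The cost is a wording change and the loss of a few subgroup displays that some readers may ask for. Data collection and clinical procedures do not change.
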